A total of 10 patients will be enrolled in the intervention (V-AD) arm of the study. These patients will be recruited from those presenting to Mayo Clinic Florida or Mayo Clinic Rochester with thoracic infections that require surgical intervention. A historic control group of 10 patients with open chest wounds who were treated with the traditional treatment techniques at Mayo Clinic will be selected using propensity-matching methods. We plan to complete our target accrual over a timeframe of approximately 12 months.

D.2. Subject Population

Subjects will be identified by the Principal Investigator or the Co-Investigators. Patients referred for surgical management of thoracic infections, who meet inclusion criteria and none of the exclusion criteria, will be invited to participate in the study. If the subject is interested in more information about

the study, a study coordinator will meet with the patient to discuss further and obtain informed consent.

D.3. Inclusion criteria

- 1. Subject provides informed consent and is:
 - a. >18 years of age,
- 2. Subject is scheduled to undergo surgical intervention(s) as part of the standard care for management of intrathoracic infection.

D.4. Exclusion criteria:

- D.4.1. Patients who have the following conditions will be excluded from participating:
 - 1. Patent bronchopleural fistulas.
 - 2. Severe respiratory failure requiring mechanical ventilation at the time of first consultation.
 - 3. Inability to provide informed consent due to physical or mental impairment.
 - 4. Altered mental status.
 - 5. Proven or suspected malignancy in the wound.
 - 6. Coagulopathy due to medical or pharmacologic reasons.
 - 7. Dependency on anticoagulants or antiplatelet medication due to high risk for adverse events if these medications are stopped for a prolonged period of time.
 - 8. Allergy to acrylic products.
 - 9. Subject is a pregnanat or lactating female

D.4.2. Patients in whom the use of V-AD is determined to be unsafe by the surgeon for any reason will be excluded from the study.

D.5. INITIAL EVALUATION AND INFORMED CONSENT FOR ENROLLMENT

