There are 2 types of foam dressings that will be used in the study:

- 1. An open pore reticulated polyurethane foam (V.A.C Granufoam Dressing)
- 2. A polyvinyl alcohol foam (V.A.C WhiteFoam Dressing).

The canister system is self-monitoring and can be set to different therapy modes (continuous or intermittent) depending on the individual patient and wound needs. In-built alarm systems can detect a loss of pressure or tubing blockage, alerting the care team to troubleshoot these issues.

G. DATA ANALYSIS

Exploratory analysis will be used to analyze the correlative studies comparing the healing rates. The analysis will include all 10 patients treated with V-AD and a matched group of 10 patients previously treated for empyema at Mayo Clinic. Due to the limited sample size the analysis will be descriptive and hypothesis generating. Any information that shows promise based on the pilot data will be explored in follow-up studies. Descriptive statistics, and scatter plots with 95% confidence intervals will graphed over time. Data will be visually inspected for differences.

The following datasets will be compared during analysis:

1. V-AD treated patients versus historical controls.

H. RISKS

H.1. Potential risks: The specific risks of V-AD use in the chest cavity have been reported and include pain, hypotension and difficulty in removing the sponge (11). No serious adverse events have been reported to date. General risks of NPWT when applied to other parts of the body include suction injury to skin and injury to underlying organs such as bowel or blood vessels. Extrapolating these adverse effects to the chest, there is an unquantifiable risk of injury to intrathoracic organs – lungs, heart, large vessels (aorta, pulmonary artery or veins). Hypothetically, injury to the lungs can lead to worsening of bronchopleural fistulas, air leaks or pulmonary hemorrhage; injury to the vascular structures can lead to significant hemorrhage, and even death. During removal of the black foam sponge dressing, it is possible to cause injury to the underlying structures due to excessive traction or adherence from tissue ingrowth.

H 1.1. Potential Severe Adverse Events

- Death
- Respiratory failure requiring ventilation (for any cause)
- Major cardiac arrhythmias requiring cardioversion or hospitalization which are hemodynamically significant.
- Massive Hemoptysis (life-threatening or requiring an intervention e.g. embolization)

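### Section G compares V-AD with the matched historical controls by eye and commits to no effect estimate, or interval for the difference, in time to closure

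*Combined protocol and SAP*

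**What the plan says.** Sections B.1 and B.2(b) make the study comparative: time to closure under V-AD against a historical Mayo Clinic cohort treated without it. Section D.1 sets the numbers: "A total of 10 patients will be enrolled in the intervention (V-AD) arm of the study", with 10 controls who "will be selected using propensity-matching methods".

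Section G is the whole analysis plan. Its elements are:

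- **Analysis set:** "The analysis will include all 10 patients treated with V-AD and a matched group of 10 patients previously treated for empyema at Mayo Clinic".
- **Status:** "Due to the limited sample size the analysis will be descriptive and hypothesis generating".
- **Display:** "Descriptive statistics, and scatter plots with 95% confidence intervals will graphed over time".
- **Method of comparison:** "Data will be visually inspected for differences".
- **Contrast:** "V-AD treated patients versus historical controls".
- **Use of the result:** "Any information that shows promise based on the pilot data will be explored in follow-up studies".

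Section G does not say which quantity the 95% intervals describe. It names no effect measure for time to closure, no interval for the V-AD versus control difference, no rule for reading the plots, and no analysis that uses the matching.

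**The concern.** A confidence interval drawn around each group answers a question about that group. It does not measure the difference between groups, and comparing two such intervals by eye is a poor substitute for the interval of the difference. Inspection can fail in two directions. A reader who waits for the intervals to separate will set aside gaps that an interval for the difference would have distinguished from zero. A reader with no rule may take a chance pattern among 20 patients as promising.

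The main useful product of a pilot of this size is an effect estimate with an honest statement of its uncertainty. Section G sends promising findings on to follow-up studies but does not commit to producing that number.

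**Working it through.** **Inputs from the documents.** 10 V-AD patients and 10 matched controls (D.1, G); 95% intervals (G). The documents give no SD, effect size, power or sample-size derivation, so there is no planned figure to reproduce.

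**Assumptions.** The outcome is roughly normal on some scale (for instance log time) with a common SD; all closure times are observed; intervals are two-sided 95% t intervals. Results are in SD units because no SD is given. Where pairs are considered, the within-pair correlation rho is set at 0, 0.3 and 0.5.

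**1. Two separate group intervals.** Each has half-width t(9)/√10 = 2.262/3.162 = 0.715 SD. They stop overlapping at an observed gap of 2 × 0.715 = 1.43 SD.

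**2. Unpaired interval for the difference.** Half-width t(18) × √(2/10) = 2.101 × 0.447 = 0.94 SD. An observed gap between 0.94 and 1.43 SD thus shows overlapping group intervals although the interval for the difference excludes zero.

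**3. Paired interval for the difference.** Half-width t(9) × √(2(1 − rho)/10):

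- rho = 0: 2.262 × √0.20 = 1.01 SD
- rho = 0.3: 2.262 × √0.14 = 0.85 SD
- rho = 0.5: 2.262 × √0.10 = 0.72 SD

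Pairing helps only if it induces correlation. At rho = 0 it costs a little (1.01 against 0.94 SD).

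**4. Over-reading.** Suppose the plots show a gap of 0.5 SD and it is called promising. The unpaired interval would run from 0.5 − 0.94 = −0.44 to 0.5 + 0.94 = 1.44 SD. The plots alone do not report this.

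**5. How often, if non-overlap were the rule.** Simulation with 100,000 runs per setting, rho = 0:

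| True difference | Non-overlap | Unpaired interval excludes zero | Paired interval excludes zero |
|---|---|---|---|
| 0 | 0.5% | 4.9% | 5.0% |
| 0.5 SD | 4% | 19% | 17% |
| 1.0 SD | 22% | 56% | 51% |
| 2.0 SD | 89% | 99% | 98% |

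At a true 1.0 SD, the paired interval excludes zero in 66% of runs at rho = 0.3 and 80% at rho = 0.5; non-overlap gives 19% and 17%.

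**6. Hazard-ratio scale.** If all 20 wounds closed, the 95% interval would be the estimate divided and multiplied by exp(1.96 × √(4/20)) = 2.4. Fewer closures would widen it.

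**7. Two paired methods that fit badly.** A within-pair log-ratio is undefined when either wound has not closed. That is plausible: Section C describes closure taking months to years, and E.1.2.3 allows V-AD to stop and patients to leave the study. A time-to-event model fully stratified by 10 pairs uses little more than which member closes first, roughly a sign test. For 9 of 10, two-sided p = 2 × (10 + 1)/1024 = 0.02; for 8 of 10, p = 2 × (45 + 10 + 1)/1024 = 0.11, so 9 are needed. At a true 1.0 SD the chance that V-AD wins a given pair is Φ(1/√(2(1 − rho))) = 0.76, 0.80 and 0.84 for rho = 0, 0.3 and 0.5. The chance of at least 9 wins in 10 is then 27%, 38% and 51%, below the 56–59% of the unpaired interval over the same rho values.

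**The case against.** The strongest defence is that Section G openly limits itself to description because the sample is small, so the absence of a test is not an error. That stands. But description does not exclude an estimate with an interval, and the plan already uses 95% intervals.

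Second, the plan states no non-overlap rule, so the 1.43 SD threshold and the detection rates above describe one assumed way of reading the plots. That also stands. The display may even be something else: intervals graphed over time would fit the serial wound dimensions recorded under E.1.2.2 as well as they fit time to closure.

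Third, descriptive statistics by group would normally let a later reader work out a crude contrast. This is partly true, but the plan does not commit to summaries that would allow it, least of all when some wounds have not closed.

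A reader might also infer that the matching is wasted. The documents do not support that. Propensity matching serves mainly to make the historical controls comparable on measured factors, and a descriptive comparison keeps that benefit. Only a possible gain in precision goes unused. The documents do not say that 1:1 pairs will be retained: D.1 and G speak of matched selection and a matched group.

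**Conclusion.** The point holds as a gap in the analysis plan. Section G commits to no effect measure and no interval for the between-group difference in time to closure, and leaves the comparison to the eye. Under the assumed non-overlap reading, the observed gap needed is about 1.5 times that for an unpaired interval (1.43/0.94 = 1.52). This rests on normality, a common SD and complete closure times. The further effect of pairing ranges from a slight loss (1.01 SD at rho = 0) to a gain (0.72 SD at rho = 0.5), and the documents do not show where in that range the study would fall.

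A stronger reading, that real differences will be missed, is not supported. It requires a rule the plan does not set, differences near 2 SD would usually show even under that rule, and inspection without a rule can err the other way. Much of the low sensitivity also belongs to the sample size: at a true 0.5 SD a formal paired interval would exclude zero only 17% to 29% of the time for rho from 0 to 0.5.

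**What to change.** In Section G, replace "Data will be visually inspected for differences" with wording such as:

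*Time to closure will be shown by group with Kaplan-Meier curves, with wounds not closed censored at last follow-up. The V-AD versus control contrast will be reported as one prespecified estimate (for example the difference in restricted mean time to closure, or a hazard ratio) with its 95% confidence interval, obtained by resampling matched pairs if 1:1 pairs are retained and by an unpaired method otherwise. It will be interpreted descriptively; plots are illustrative.*

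The final text should pick one measure. If it is the restricted mean, it should also fix the time horizon in advance, within the follow-up available in both groups. Full matched-set stratification and within-pair log-ratios should not be the main method, for the reasons in step 7 of the working.

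The cost is a short rewrite, with no new patients. The analysts must record whether pairs are kept and the last follow-up date for wounds that do not close. The downside is a wide interval at 10 versus 10, perhaps slightly wider still with a paired method if matching induces no correlation. The change makes the uncertainty visible but does not reduce it.

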After obtaining informed consent from eligible patients, they will be taken to the operating room for the initial assessment and treatment as determined by the surgeon. The intervention may include, but is not limited to, thoracotomy, minimally invasive thoracic surgery, washout, excisional debridement, pulmonary decortication, pulmonary resection and closure of any obvious bronchopleural fistulas. Aerobic and anaerobic tissue cultures from the infected space will be obtained at the time of surgery. The surgeon will determine if the chest can be closed primarily. If unable to do so due to obvious infection or perceived high risk of developing a subsequent deep space abscess, the surgeon will next assess whether the wound is suitable for management with V-AD (V.A.C.* Therapy, KCI, San Antonio, TX). In the absence of any contraindications, the OCW will then be packed with one or more foam sponges and an airtight transparent dressing. At the time of application, these sponge dressings can be cut to fit within the wound. The type of dressing (black or white foam) to be used will be determined by the surgeon depending on the characteristics of the wound bed. The dressing will then be connected to the negative pressure canister unit and maintained on continuous negative pressure ranging from -75 mmHg to -125 mmHg. Unless otherwise indicated, the dressing will be changed once every 72 hours under IV sedation or anesthesia.

The patient will be admitted to the hospital for at least two supervised dressing changes, at which time the surgeon will re-assess the wound to determine if it can be closed with or without a soft tissue (muscle, omentum, etc.) flap. Wounds determined to be not ready for closure will then be repacked with the V-AD. If no other indication for inpatient hospital care exists other than the V-AD, the patient will be then discharged home or to a skilled nursing facility where the remainder of dressing changes will be performed. If the patient cannot be safely discharged from the hospital, inpatient care will be continued.

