After discharge, the patient will return to the outpatient clinic for wound inspection and dressing change by the surgeon once every two weeks and earlier, if necessary. During hospitalization and clinic visits, a Mayo Clinic photographer or a provider authorized to use the Mayo Clinic imaging software will photograph the wound, which will be a part of the permanent medical record of the patient. At every dressing change in and outside the hospital, the number of individual pieces of foam sponges will be entered in a logbook and accounted for during removal at the next change.

Figure 1: Algorithm for Patient Selection and Enrollment

E.1.2.2. Monitoring:

A prospective database of all patients in the study will be maintained and will record the following:

- a. Name, Medical Record number and Dates of dressing changes
- b. Pain scores visual analogue scores,
- c. Ease of dressing changes (Easy, moderately difficult, very difficult)
- d. Wound bed characteristics including amount of granulation tissue (minimal, moderate and significant) and dimensions (length x breadth x depth in centimeters).
- e. Duration of treatment
- f. Adverse events

E.1.2.3. Discontinuation of V-AD therapy:

1. In the absence of a noticeable improvement in the wound bed after 2 weeks of continuous V-AD therapy, the treatment plan will be re-assessed and the determination will be made as to whether the V-AD therapy should be discontinued.

2. The V-AD will be discontinued if the patient develops severe uncontrolled pain that does not respond to pain medications or a reduction in the negative pressure to -50 mm Hg.

3. In the event of any unpredicted adverse event, such as bleeding, injury to underlying organs, new onset of respiratory distress or allergy to the dressings will result in removing the V-AD.

4. Patients who require treatment with anticoagulation or antiplatelet agents after V-AD application will be removed from the study to avoid hemorrhagic complications.

F. DRUGS/ SUBSTANCES/ DEVICES

The V.A.C. Therapy System has many components that work together to apply negative pressure to wounds. The components include:

- 1. a porous foam dressing which comes in contact with the wound base and equally distributes negative pressure throughout the wound,
- 2. an airtight transparent adhesive drape that covers the foam dressing and
- 3. a software-controlled V.A.C Canister that is connected to the dressing by means of a transparent plastic tubing.

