- Intra-parenchymal/intrapleural hemorrhage leading to hemodynamic instability or requiring any intervention to specifically address the bleeding.
- All new onset bronchopleural fistulas will be reported as SAE's.
- Worsening of pleural space infection requiring treatment with IV antibiotics, with exceptions as below:
 - Treatment of pathogens identified on microbiology obtained during the initial culture will not count as a new infection.
 - Requirement for sharp debridement of necrotic tissue or exudates identified during dressing changes will not be considered an adverse event, as this is normal during management of infected wounds.

H.1.2. Other Adverse Events

- Minor cardiac arrhythmias NOT requiring cardioversion, hospitalization and/or are NOT hemodynamically significant.
- Minor Hemoptysis or minor intra-parenchymal/intrapleural hemorrhage
- Pneumonia/pleural space infection treated as outpatient
- Mild (<4/10, not requiring IV medication) to moderate pain (requiring IV medication or rated as >5/10)
- DVT or Pulmonary Embolus treated with anticoagulation alone

H.2. Risk Prevention and Monitoring: In order to decrease the risks of these potential adverse events, the following safety precautions will be taken:

- 1. The dressings will not be applied directly in contact over any exposed blood vessels, heart or lung, or anastomotic sites.
- 2. Mepitel[®] (Mölnlycke Health Care, Norcross, GA), a silicone-based perforated non-adherent dressing will be placed over any delicate organs such as the heart or the lung. This will prevent adherence of the foam dressing to the underlying tissue while allowing drainage. Mepitel[®] itself can be easily removed as it is non-adherent.
- 3. The black foam dressing will not be used directly over any organ/structure likely to be traumatized during removal of the dressing. Instead, the white foam will be used as the first layer. The black foam may be placed over the white foam in such instances.
- 4. Prior to removal, the dressings will be thoroughly soaked with normal (0.9%) saline to disengage the dressings easily.

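### The initial-culture exception in H.1.1 leaves open whether same-organism worsening is a severe event, and H.3.1 and H.3.4 start the 24-hour report at different times.

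*Combined protocol and SAP*

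**What the plan says.** **Severe-event list.** H.1.1 includes "Worsening of pleural space infection requiring treatment with IV antibiotics, with exceptions as below". The first exception reads "Treatment of pathogens identified on microbiology obtained during the initial culture" and continues "will not count as a new infection". A second exception says that sharp debridement at dressing changes is not an adverse event at all.

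**Other-event list.** The infection item in H.1.2 is "Pneumonia/pleural space infection treated as outpatient".

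**Who is exposed to the exception.** Inclusion criterion 2 (D.3) is "Subject is scheduled to undergo surgical intervention(s) as part of the standard care for management of intrathoracic infection". Section E.1.2.1 adds: "Aerobic and anaerobic tissue cultures from the infected space will be obtained at the time of surgery".

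**Use of the severe label.** H.2 defines safety by the rate of severe adverse events and points the reader to text that follows. H.3.1 sends severe events to the DSMB and puts the study on hold for every SAE until the DSMB has reviewed it.

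**Reporting time.** H.3.1 asks for an immediate report, and at the latest 24 hours after the investigator recognizes or classifies the event as severe. H.3.4 requires the safety board to be notified within 24 hours of the event occurring.

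**Contacts after discharge.** E.1.2.1 sets dressing changes every 72 hours by default, with the remaining ones done at home or in a skilled nursing facility. It also schedules clinic attendance for "wound inspection and dressing change by the surgeon once every two weeks and earlier, if necessary". H.2 allows adverse-event data to be collected by telephone and gives no frequency.

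**The concern.** The H.1.1 item is about worsening, while its exception is about newness. The exception carries a limit on organism and none on time, severity or clinical course. Every participant enters with an intrathoracic infection and has cultures taken at surgery, so the clause could come into play for any patient whose initial culture is positive.

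Whether the presenting infection worsens under V-AD is an obvious safety question for this trial. If the exception is applied to such an event, it may not reach the DSMB as a severe event and may not trigger the hold.

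The two reporting clocks are a separate problem. They leave the investigator with one limit that cannot always be met, and the protocol does not say which limit governs.

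**Working it through.** The documents state no expected severe-event rate and no safety calculation, so there is no figure to reproduce. The check sets the sections side by side, with simple arithmetic for the clock.

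**1. The two readings of the exception.**

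- *Narrow.* Continuing to treat organisms already found at surgery is not a new event. True worsening still counts under H.1.1.
- *Broad.* The clause is introduced as an exception to the worsening item. Worsening treated with IV antibiotics is therefore removed when the organism was in the initial culture. In support of this reading, continued treatment without worsening never met the parent item, so on the narrow reading the clause clarifies but removes nothing.

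**2. A test case.** Take a patient whose pleural infection worsens with the original organism and who receives IV antibiotics in hospital, with none of the other H.1.1 events.

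| Section | Narrow reading | Broad reading |
|---|---|---|
| H.1.1 severe list | included | excepted |
| H.1.2 other list | not needed | not included, because the infection item is limited to outpatient treatment |
| H.3.1 documentation of all observed AEs | applies | applies |
| H.3 judgement or CTCAE 4.0 grading | available | available, but nothing says whether it overrides the exception |

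The event is recorded on either reading. Only its severe label changes.

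**3. Which text feeds the severe-event rate.** H.2 points upward to the listed events when it commits to monitoring and reporting, and downward when it defines the safety rate. What lies below is H.3, which works by the investigator's judgement and CTCAE grade. H.1.1 lies above and is titled as a list of potential events. The text does not settle which of the two supplies the count.

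**4. The clock.** Let d be the hours from occurrence to recognition.

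- H.3.1 deadline, counted from occurrence: d + 24 hours.
- H.3.4 deadline, counted from occurrence: 24 hours.
- Difference between the deadlines: (d + 24) − 24 = d.
- If d is more than 24, the H.3.4 deadline has passed before anyone could report.

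Suppose, as an assumption, that an event starts just after a dressing change and is first noticed at the next one, so d = 72. The H.3.4 limit was then missed by 72 − 24 = 48 hours at the moment of recognition. H.3.1 still allows a report up to 72 + 24 = 96 hours after occurrence. An earlier visit or a telephone call would shorten d. An event seen only at a two-weekly surgeon visit could have a longer d.

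**The case against.** The case for the narrow reading is strong. The exception speaks of treatment and says only that it is not a new infection; it does not say that worsening is disregarded. The debridement exception that follows shows how the authors wrote a full exclusion when they wanted one.

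There are also backstops. Death, ventilation for any cause, the listed haemorrhage and new bronchopleural fistula count whatever the organism. H.2 and H.3.1 require lesser complications and all observed adverse events to be recorded, and the investigator may still judge the event severe. The analysis in section G is descriptive, and no safety threshold depends on the rate.

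A reader might infer more than the documents support:

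- *That the protocol excludes same-organism worsening.* It does not say so; the wording only permits that application.
- *That such events would go unrecorded.* H.3.1 and the adverse-event field in the study database (E.1.2.2) argue against this.
- *That investigators at the two campuses would count differently.* H.3.4 gives identification and grading to the principal investigator.
- *That two weeks is the longest scheduled gap between contacts.* It is the interval between surgeon visits; dressing changes fall every 72 hours by default.
- *That confidence intervals for a few events in 10 patients measure this defect.* They would be the same for any binary outcome in 10 patients.

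What stands is that the lead-in labels the clause an exception to worsening, so the broad application remains open. The two clocks conflict on any reading.

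**Conclusion.** The point holds as an ambiguity in the severe label plus a direct inconsistency in reporting time. It is worth correcting, because the label decides DSMB reporting and the study hold.

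The size of the first part cannot be estimated, because the documents give no frequency for same-organism worsening. One relabelled patient among the 10 V-AD patients would move the severe-event rate by 1/10, or 10 percentage points. That rests on two assumptions the text does not confirm: that the rate is per patient, and that H.1.1 feeds it.

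The second part does not alter the rate. H.3.4 cannot be met for any event found more than 24 hours after it occurs, and this can happen with contacts 72 hours apart (72/24 = 3 times the limit). How often it would happen is not known.

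**What to change.** 1. Reword the H.1.1 exception so that it covers only continued treatment of the presenting infection without worsening. Worsening that meets the H.1.1 item is then counted for reporting whatever the organism.
2. State in H.2 which source defines the severe-event rate: the H.1.1 list, or judgement and grading under H.3.
3. Reconcile H.3.1 and H.3.4 to one reporting clock that can be met for events found late.

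These are changes to wording on counting and reporting, with no new data collection. The downside is a possibly higher reported severe-event count and more study holds. Some judgement will remain, because H.1.1 does not define worsening.

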- 5. The number of individual pieces of foam dressing placed during each dressing change will be documented and care will be taken to ensure that the same number of dressings is removed (and documented). In case there is a discrepancy in the tally of foam pieces placed and removed in consecutive dressing changes, the surgeon will be contacted immediately. V-AD will not be reapplied until the surgeon confirms that no foam piece has been retained in the wound by personally examining the wound.

We plan to monitor and report all of the above adverse events from the first application of the V-AD to one week after final closure of the wound or termination of V-AD therapy. All standard precautions will be taken to minimize risk. Patients will be monitored in a telemetry unit during hospital admission for complications including bleeding, hemodynamic instability (heart rate < 60 or > 120, systolic BP <90 or > 150, diastolic BP < 50 or > 100, respiratory compromise (SpO2 < 92% on room air).

All data regarding risk/adverse events will be collected in person while the patient is admitted to the hospital or seen in clinic or over the telephone if the patient is outpatient.

The primary endpoint of this study is efficacy of treatment. However, safety is also a critical component and will be defined by the rate of severe adverse events (see below). In addition to major complications, all intermediate and minor complications will also be recorded.

H.3. Evaluation and Grading of Adverse Events

H.3.1. Performing Adverse Events Assessments

The Principal Investigator will be responsible for promptly documenting and reporting all adverse events (AEs) observed during the study. If the AE is considered severe, the investigator must report the AE immediately to the DSMB through Mayo Clinic Rochester. All AEs considered "severe" will be reported no later than 24 hours after the investigator recognizes/classifies the event as a severe adverse event.

For all SAE's, the study will be placed on hold until the DSMB has reviewed and notification received to continue study accrual. The safety monitoring board may require study protocol modifications or cessation of all study activities prematurely.

H.3.2. Adverse Event Definitions

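### The only stated trigger for suspected retained foam is a mismatch in the piece count, and a piece that comes out incomplete but is counted as one does not produce a mismatch

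*Combined protocol and SAP*

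**What the plan says.** Retained foam is addressed in two places in the protocol, and both are counts.

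- **Section E.1.2.1 (logbook).** At every change, in or out of hospital, "the number of individual pieces of foam sponges will be entered in a logbook and accounted for during removal at the next change".
- **Section H.2, item 5.** Pieces placed are documented and the same number must come out. If there is "a discrepancy in the tally of foam pieces placed and removed in consecutive dressing changes, the surgeon will be contacted immediately". The hold follows: "V-AD will not be reapplied until the surgeon confirms that no foam piece has been retained in the wound by personally examining the wound".

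Other provisions bear on how the count works in practice, all in E.1.2.1 unless noted.

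- Foam is shaped by hand: "these sponge dressings can be cut to fit within the wound".
- Unless otherwise indicated, "the dressing will be changed once every 72 hours under IV sedation or anesthesia".
- The surgeon re-assesses the wound at the supervised inpatient changes, of which there are at least two. A patient with no other need for inpatient care is then "discharged home or to a skilled nursing facility where the remainder of dressing changes will be performed".
- After discharge the patient attends clinic for "wound inspection and dressing change by the surgeon once every two weeks and earlier, if necessary".
- E.1.2.2 has the database record how easy each change was (item c) and, in item d, "Wound bed characteristics including amount of granulation tissue (minimal, moderate and significant) and dimensions". Neither item mentions foam.
- H.2 also provides for saline soaking before removal, a silicone non-adherent layer over delicate organs, and white foam as the first layer where removal could cause trauma.

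**The concern.** Item 5 exists so that V-AD is not put back over foam still lying in an infected chest cavity. The protocol takes that hazard seriously enough to stop treatment until the surgeon has personally looked. That response depends on one signal, an unequal count. A count detects a whole piece left behind. It does not detect part of a piece left behind when the rest has come out and been counted as one.

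What is at stake is patient safety at changes where the surgeon is not present. At such a change an equal tally satisfies the written rule whether or not removal was complete, and nothing in the rule asks anyone to judge completeness.

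**Working it through.** No sample size, power or event figure is involved and the plan states no figure to reproduce. The check is a reading of the text with one piece of simple arithmetic.

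**1. Does the count detect an incomplete piece?** Let *k* be the number placed at one change.

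| Situation at the next change | Placed | Counted out | Item 5 triggered? |
|---|---|---|---|
| All pieces out whole | *k* | *k* | No |
| One whole piece left behind | *k* | *k* − 1 | Yes |
| One piece out incomplete, counted as one | *k* | *k* | No |
| Fragment found and counted at a later change, with *m* newly placed | *m* | *m* + 1 | Yes, but only after at least one reapplication over it |

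The third row is the gap. The fourth shows that the count may correct itself late.

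**2. Does another provision check that removal is complete?**

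- Soaking, the non-adherent layer and white foam (H.2, items 2 to 4) make adherence less likely. They do not verify removal.
- Ease of change and wound-bed characteristics (E.1.2.2, items c and d) could prompt suspicion. No action on foam is tied to them.
- The inpatient re-assessment is made to decide on closure, and the clinic visit is for wound inspection. Either may reveal a fragment, but neither is specified as a foam check.
- Adverse-event data on outpatients may be taken by telephone (H.2), which does not by itself include a look at the wound.

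**3. Are there changes without the surgeon?** E.1.2.1 places the remaining changes after discharge at home or in a nursing facility and does not say who does them. Item 5 itself has the surgeon contacted, which presupposes changes at which the surgeon is absent. *If* the 72-hour interval continues after discharge and each clinic change restarts the clock, 14 / 3 = 4.67, so four changes (days 3, 6, 9 and 12) fall between scheduled visits. The protocol does not confirm that assumption: the same sentence calls for sedation or anesthesia and does not explain how that applies at home. The figure shows only where the gap would lie; the argument needs only that some changes happen without the surgeon.

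**4. Is incomplete removal plausible on the documents?** Section C reports difficult removal because of impaction. H.1 lists difficulty in removing the sponge as a reported risk in the chest, and warns that black foam may adhere through tissue ingrowth. H.1 names injury to underlying structures as the consequence, not loss of foam. Tearing is therefore an inference, and no rate is given.

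**The case against.** The strongest case against the point has four parts.

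- **The failure is not in the documents.** No section mentions foam tearing, and the traction warning concerns harm to tissue. This stands as a limit: the inference is reasonable, but no frequency can be attached to it.
- **Counting is not the only protection.** A reader might infer that nothing except the tally could reveal a fragment. The documents do not support that. The surgeon sees the wound at the supervised inpatient changes and every two weeks after discharge, or earlier if needed. H.1.1 presumes that necrotic tissue can be identified at changes, H.2 adds a general commitment to standard precautions, and nothing forbids calling the surgeon about a visibly torn piece. What remains is narrower: the count is the only *explicit, foam-specific* trigger.
- **The benefit is uncertain.** The person doing the change would also complete the new entry, and someone who overlooks a tear may record the piece as whole. This is partly right. A required look and a written instruction make detection and a call more likely; they do not guarantee either.
- **Extra holds could interrupt therapy.** Foam is cut to fit, so wholeness can be hard to judge. A rule that stopped V-AD at every doubt could cause avoidable interruptions, and time to closure is the main comparison (B.2, aim b). This is a fair objection to an over-strict rule, so a hold should follow automatically only from a visible tear or an incomplete piece, with doubtful cases left to the surgeon.

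**Conclusion.** The point holds as a cheap improvement to patient safety. The stated response to retained foam follows only from an unequal count, and an incomplete piece counted as one leaves the count equal. The surgeon's scheduled inspections are a real but incidental backstop, so the gap lies mainly at changes outside hospital between visits.

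Two assumptions carry this: that foam can come out incomplete, and that some changes take place without the surgeon. The first is inferred; the second follows closely from E.1.2.1 and the wording of item 5.

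Two stronger readings are not supported. A reader might turn the visit schedule into a number of days for which foam would lie undetected and treat that as a size of risk. That would rest on an unconfirmed interval after discharge and on nobody noticing sooner, and there is no rate to multiply it by. A reader might also infer that the efficacy comparison or the safety record is undermined. Neither follows: the gap changes no endpoint or comparison, and a fragment that is discovered could be recorded under the adverse-event definition in H.3.2 and the commitment in H.2 to record lesser complications.

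**What to change.** Make three small changes, applying in and outside hospital.

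1. At each change, before repacking, inspect the removed pieces and the visible cavity.
2. Add one entry to the existing logbook: all pieces removed whole, yes or no.
3. Amend H.2, item 5 so that a visibly torn or incomplete piece is handled like a tally discrepancy: the surgeon is called at once and V-AD is withheld until the surgeon has examined the wound. If the person doing the change is unsure, they call the surgeon, who decides whether an examination is needed.

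The foam is already removed, counted and logged at every change, so the routine cost is one entry per change in 10 V-AD patients and an amended sentence. The downside is occasional extra calls, unscheduled examinations after discharge, or short interruptions of V-AD. How often cannot be predicted, because the documents give no rate of incomplete removal. Leaving unsure cases to the surgeon's judgement is meant to keep interruptions few.
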